#### **Ethical aspects**

This is an international observational study, it will not attempt to change or modify the clinical practice of the participating physicians. The study will meet and conform to the standards outlined in the Declaration of Helsinki and Good Epidemiological Practices. Every clinical center attending the study is responsible for Ethics Committee approval depending on the local policy for observational and noninterventional studies. All surgeons involved in the patients' recruitment will be included in the research authorship.

#### **Publication policy**

The Local Lead and two Collaborators from each center will be listed as Co-authors in the final publications. Data will be published as a pool from all participating surgical units. Data emerged from the MANCTRA-1 study will be published irrespective of findings. Results will be published on ClinicalTrials.Gov and each manuscript that is generated based on the registry will be disseminated to all participating centers before final publication.

#### Safety issues

None.

#### **Data collection**

In each centre, the coordinator will collect and compile data in an online case report system. Data will be recorded contemporaneously on a dedicated, secure server that allows collaborators to enter and store data in a secure system. No patient identifiable data (name, date of birth, address, telephone number, etc.) will be recorded.

#### **Informed consent**

Due to its retrospective design, this observational study will not attempt to change or modify the laboratory or clinical practices of the participating physicians. Consequently, informed consent will not be required.

#### Data management

Every local investigator is responsible for entering data on an on line case report form for every patient included in the study.

## Funding

This research has not received any specific grant from funding agencies in the public, commercial, or not-for-profit sectors.

## **Financial and Insurance**

Not applicable.

## Analyzed Data – CRF -

#### Section 1 – General Informations

- ! Country
- ! Name and Surname of the Local Lead
- ! Email address of the local lead
- ! Name and Surname of the Local Collaborator
- ! Email address of the Local Collaborator

## Section 2 – Demographic Characteristics

- ! Year of hospital admission for acute biliary pancreatitis (2019 Vs. 2020)
- ! Patient age
- ! Sex (Female Vs. Male)
- ! Covid-19 status on admission (Negative/Positive/Untested)

- ! Previous episodes of biliary pancreatitis (Yes/No)
- ! Admitting speciality (HPB surgery/General Surgery/Internal Medicine/Gastroenterology)

#### Section 3 – Comorbidity

- ! Charlson's comorbidity index
- ! Body Mass Index BMI
- ! Clinical history of diabetes (No diabetes/Diabetes with organ disfunction/Diabetes without organ disfunction)
- ! Clinical history of chronic pulmonary disease other than Covid-19 pneumonia (Yes/No)
- ! Clinical history of hypertension (Yes/No)
- ! Clinical history of atrial fibrillation (Yes/No)
- ! Clinical history of ischemic hearth disease (Yes/No)
- ! Clinical history of chronic kidney disease (Yes-under medications/Yes-in permanent renal replacement therapy or in preparation for it/No)
- ! Clinical history of diseases of the hematopoietic system (Yes/No)
- ! Patient on immunosuppressive medications on hospital admission (Yes/No)

#### Section 4 – Clinical Scores

- ! Glasgow Coma Scale (GCS)
- ! qSOFA
- ! WSES (World Society of Emergency Surgery) sepsis score
- ! BISAP (Bedside Index of Severity in Acute Pancreatitis) score
- ! ASA score (1-2-3-4-5)
- ! Glasgow-Imrie score
- ! Ranson's score
- ! Apache II score
- ! Revised Atlanta Classification (Mild acute pancreatitis/Moderately severe acute pancreatitis/Severe acute pancreatitis)
- ! Organ failure during the hospital stay (None/Cardiovascular/Respiratory/Renal)

#### Section 5 – Vital signs on admission

- ! Temperature
- ! Systolic blood pressure
- ! Hearth rate
- ! Respiratory rate
- ! Blood oxygen saturation
- ! ICU admission during the hospital stay (Yes/No)

#### Section 6 – Laboratory tests on admission

- ! WBC
- ! Neutrophils
- ! Platelets
- ! INR (International Normalized Ratio)
- ! C-reactive protein
- ! Aspartate aminotransferase AST
- ! Alanine aminotransferase ALT
- ! Total bilirubin
- ! Conjugated bilirubin
- ! Gamma-glutamil-transpeptidase GGT
- ! Serum amylase
- ! Serum lipase
- ! Lactate DeHydrogenase LDH
- ! Procalcitonin PCT
- ! Lactates

#### Section 7 – Diagnostic Imaging

! Initial diagnostic imaging (Ultrasound scan on admission/CT scan on admission/CT scan <24h/CT scan 24-48h/CT scan >48h)

- ! MRCP (MRCP on admission/MRCP <24h/MRCP >24h/No)
- ! Endoscopic ultrasound scan (Yes <24 hours/Yes >24 hours/No)
- ! Re-evaluation with CT scan (None/<7 days/7-14 days/15-30 days/>30 days)

Section 8 – Physical examination on admission (Localized abdominal pain/Localized abdominal rigidity/Diffuse abdominal pain/Diffuse abdominal rigidity/No abdominal pain/No abdominal rigidity)

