#### Secondary outcomes

- ! Early definitive treatment rate in 2019 vs. 2020: defined as treatment in accordance with the current guidelines (cholecystectomy or ERCP with endoscopic sphincterotomy during the same hospital admission or within 2 weeks of discharge)
- ! 30-day hospital readmission rate in 2019 vs. 2020: defined as hospital readmission within 30days from discharge for recurrent biliary AP while awaiting interval cholecystectomy, or due to post-cholecystectomy complications
- ! Predictive factors of morbidity and mortality in patients with biliary AP

The compliance of surgeons to the most up-to-date international guidelines on biliary AP will be assessed through the analysis of the following attitudes:

! Use of scoring systems for the diagnosis and severity grading of biliary AP

- ! Use of lipase dosage (for the diagnosis) and CRP (for the severity grading) during the diagnostic workup
- ! Use of Ultrasound scan, CT scan, MRCP, and endoscopic Ultrasound scan (EUS) in the correct way and timing
- ! Use of early ERCP and sphincterotomy in case of cholangitis and/or choledocholithiasis
- ! Use of percutaneous and/or endoscopic drainage in case of infected pseudocyst or necrosis
- ! Timing of surgical necrosectomy
- ! Timing of re-laparotomy in case of open abdomen strategies
- ! Use of prophylactic antibiotics/antifungals
- ! Use of somatostatin analogs
- ! Use of early enteral feeding
- ! Use of early definitive treatment strategies, including cholecystectomy and/or ERCP and sphincterotomy

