## Table\_1: Statements and Recommendations from the 2019 WSES guidelines for the management of Acute Pancreatitis patients.

1. Severity grading	! ! !	Severe acute pancreatitis is associated with persistent organ failure (cardiovascular, respiratory, and/or renal), and high mortality. Both new classification systems, Revised Atlanta Classification and Determinant-based Classification of Acute Pancreatitis Severity, are similar in establishing the diagnosis and severity of acute pancreatitis (1C). Patients who have persistent organ failure with infected necrosis have the highest risk of death (1C). Patients with organ failures should be admitted to an intensive care unit whenever possible (1C).
2. Imaging	! ! !	On admission, ultrasound (US) should be performed to determine the etiology of acute pancreatitis (biliary) (1C). When doubt exists, computed tomography (CT) provides good evidence of the presence or absence of pancreatitis (1C). All patients with severe acute pancreatitis need to be assessed with contrast-enhanced computed tomography (CE-CT) or magnetic resonance imaging (MRI). Optimal timing for first the CE-CT assessment is 72–96 h after onset of symptoms (1C). Magnetic resonance cholangiopancreatography (MRCP) or endoscopic ultrasound should be considered to screen for occult common bile duct stones in patients with unknown etiology (1C).
3. Diagnostic laboratory parameters	! ! ! !	The cut-off value of serum amylase and lipase is normally defined to be three times the upper limit. C-reactive Protein level $\geq 150$ mg/l at third day can be used as a prognostic factor for severe acute pancreatitis (2A). Hematocrit > 44% represents an independent risk factor of pancreatic necrosis (1B). Urea > 20 mg/dl represents itself as an independent predictor of mortality (2B). Procalcitonin is the most sensitive laboratory test for detection of pancreatic infection, and low serum values appear to be strong negative predictors of infected necrosis (2A). In the absence of gallstones or significant history of alcohol use, serum triglyceride and calcium levels should be measured. Serum triglyceride levels over 11.3 mmol/l (1000 mg/dl) indicate it as the etiology (2C).
4. Diagnostics in idiopathic pancreatitis	!	In idiopathic pancreatitis, biliary etiology should be ruled out with two ultrasound examinations, and if needed MRCP and/or endoscopic ultrasound EUS, to prevent recurrent pancreatitis (2B).

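### Admission ultrasound and first CT are options of one CRF field with no selection rule and no 'not done' code, so compliance with either may not be measurable

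*Combined protocol and SAP*

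**What the plan says.** CRF Section 7 (Diagnostic Imaging) has one field for the first imaging test: "Initial diagnostic imaging (Ultrasound scan on admission/CT scan on admission/CT scan <24h/CT scan 24-48h/CT scan >48h". One option is ultrasound and four are CT at different times. There is no option for both tests, none for ultrasound later or not done, and none for CT not done.

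The other tests in the same section are handled differently. Each has its own field with a negative code: "MRCP (MRCP on admission/MRCP <24h/MRCP >24h/No", "Endoscopic ultrasound scan (Yes <24 hours/Yes >24 hours/No" and "Re-evaluation with CT scan (None/<7 days/7-14 days/15-30 days/>30 days". The last covers repeat CT only. No other CRF section records abdominal ultrasound.

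The Secondary outcomes section lists among the compliance items "Use of Ultrasound scan, CT scan, MRCP, and endoscopic Ultrasound scan (EUS) in the correct way and timing". Table 1, item 2, gives the recommendations behind that item. For ultrasound: "On admission, ultrasound (US) should be performed to determine the etiology of acute pancreatitis (biliary) (1C". For CT at diagnosis: "When doubt exists, computed tomography (CT) provides good evidence of the presence or absence of pancreatitis (1C". For severe disease: "All patients with severe acute pancreatitis need to be assessed with contrast-enhanced computed tomography (CE-CT) or magnetic resonance imaging (MRI", with the first contrast CT placed at 72-96 h after onset of symptoms.

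**The concern.** The protocol wants ultrasound and CT judged separately, but the form treats them as alternatives. A severe patient imaged as Table 1 describes, with ultrasound on admission and CT later, fits two options of the same field, and nothing says which one to enter.

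Two things are at stake. The first is the compliance rate for each test, a secondary objective. The second is the primary objective, which relates disregarded guideline items to bad outcomes. If patients with both tests tend to be the sicker ones and are stored under CT, the apparent 'no ultrasound' group fills with patients at higher risk of death for reasons unrelated to ultrasound.

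**Working it through.** The plan gives no figure to reproduce here. The check has a structural part and an illustration.

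**Structure.** Suppose one answer is stored for a patient who had both tests.
- Stored as CT: the admission ultrasound leaves no trace, so a derived ultrasound item can score it as missed.
- Stored as ultrasound: the first CT and its time class leave no trace. The repeat-CT field does not recover them.
- With no 'not done' code, non-use of ultrasound can be inferred only from a CT answer or a blank.

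**Inputs from the Sample size section.** Severe disease is 20% of presentations with 30% mortality; overall mortality is about 10%. Non-severe mortality is therefore (0.10 − 0.20 × 0.30) / 0.80 = 0.05.

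**Assumed inputs, not in the documents.** True admission ultrasound is 95% in both severity classes, with no effect on death. CT is done in a share c of patients, independently of ultrasound: 20-40% if non-severe, 50-80% if severe. A share q of both-test patients is entered as CT (1 or 0.5), and any patient not recorded under ultrasound is scored as 'no ultrasound'.

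**Formulas.** Within a class, recorded ultrasound R = 0.95 × (1 − c × q). Overall R = 0.2 × R(severe) + 0.8 × R(non-severe). Mortality among those recorded with ultrasound is [0.2 × R(severe) × 0.30 + 0.8 × R(non-severe) × 0.05] / R. For 'no ultrasound', replace each R by 1 − R. The crude odds ratio compares these two mortalities.

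**Worked corner.** Take q = 1, CT 80% severe and 20% non-severe.
- R(severe) = 0.95 × 0.20 = 0.19; R(non-severe) = 0.95 × 0.80 = 0.76; R = 0.038 + 0.608 = 0.646.
- Mortality with recorded ultrasound = (0.0114 + 0.0304) / 0.646 = 6.5%.
- Mortality with 'no ultrasound' = (0.2 × 0.81 × 0.30 + 0.8 × 0.24 × 0.05) / 0.354 = (0.0486 + 0.0096) / 0.354 = 16.4%.
- Odds ratio = (0.164 / 0.836) / (0.065 / 0.935) ≈ 2.8.

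| CT severe / non-severe | Recorded ultrasound, q = 1 | Odds ratio, q = 1 | Recorded ultrasound, q = 0.5 | Odds ratio, q = 0.5 |
|---|---|---|---|---|
| 50% / 20% | 70% | 1.76 | 83% | 1.49 |
| 50% / 40% | 55% | 1.19 | 75% | 1.12 |
| 80% / 20% | 65% | 2.84 | 80% | 1.98 |
| 80% / 40% | 49% | 2.01 | 72% | 1.48 |

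**Checks.**
- With separate fields (q = 0), recorded ultrasound is 95% and the odds ratio is 1.00.
- If the share of ultrasound patients stored as CT is the same in both classes, the recorded rate still falls but the odds ratio stays at 1.00.
- With a reversed gradient (20% of severe and 40% of non-severe ultrasound patients stored as CT, true ultrasound 80-95%), the odds ratio is 0.69-0.75.
- Within a severity class, mortality is the same whatever is recorded (30% or 5%), so the class-specific odds ratio is 1.00.

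**The opposite error, same assumptions.** True CT use is 0.2 × 0.50 + 0.8 × 0.20 = 26% at the lowest and 0.2 × 0.80 + 0.8 × 0.40 = 48% at the highest. If every both-test patient is entered as ultrasound, only CT patients without ultrasound (5%) remain under CT: 0.05 × 26% = 1.3% to 0.05 × 48% = 2.4%.

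**The case against.** The strongest reply is that single choice is nowhere stated. The CRF in the protocol is a printed list of variables, not the live form. Section 8 uses the same slash layout for examination findings that can coexist, and Section 4 does so for organ failures. If several answers were allowed and centres chose all that applied, both tests are on record. This stands, so the point has to be conditional. It does not clear the form: no instruction is printed, and an unselected ultrasound would still not separate 'not done' from 'not entered'.

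A second reply is that 'initial' suggests the first test. An admission ultrasound followed by CT would then be entered as ultrasound, and ultrasound compliance would be right. That also stands, but the first CT and its timing, which belong to the same compliance item, are then lost.

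A reader might go further and infer that ultrasound compliance will be understated, and that the study will report higher mortality when ultrasound is disregarded. The documents do not support that:
- No rule for scoring ultrasound compliance is given, so counting a CT entry as a missed ultrasound is one possible derivation.
- The severity gradient is an inference. Table 1 accepts MRI instead of CT in severe disease, and its contrast CT at 72-96 h need not displace an initial ultrasound.
- The odds ratios above are unadjusted. The CRF collects Revised Atlanta class, organ failure and severity scores, the primary objective is framed by clinical presentation, and logistic models are planned. The Statistical analysis section names no severity adjustment, but nothing rules it out.

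**Conclusion.** The concern holds as a weakness of data capture. One shared field, without a selection rule or 'not done' codes, cannot be relied on to measure two tests that the protocol says it will assess separately. If one answer is stored, each both-test patient loses either the ultrasound or the first CT, and the documents do not settle which.

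On the stated assumptions, recorded ultrasound would be 49-70% against a true 95% if all both-test patients are entered as CT, with a crude odds ratio for death of 1.2-2.8. If half are entered as CT, the figures are 72-83% and 1.1-2.0. These show possible size only: the ultrasound rate, the CT rates and the share entered as CT are all assumed. Adjusting for severity class removes the odds ratio in this model, but no adjustment recovers the true ultrasound or CT rates, because the information was never collected. A false mortality signal is therefore a possibility in an unadjusted analysis, not a predicted result. One compliance item among several is affected, so the change is worth making but does not threaten the study as a whole.

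**What to change.** Replace the shared field by two, both answered for every patient: 'Ultrasound (on admission / later / not done)' and 'First CT (time class / not done)'. Score each compliance item from its own field and write that rule into the analysis section. The cost is one extra CRF field and slightly longer data entry.

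The Study periods section has entry running from 01/03/2021 to 31/08/2021. If it has closed, the sponsor should state whether the live form took one answer or several and what centres were told to enter. Unless both tests can be shown to have been captured, report ultrasound and first-CT compliance as not reliably measured.

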#### Primary objective

! To evaluate which items of the current AP guidelines, if disregarded, correlate with

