## Section 10 – 30-day Morbidity

- ! Gastric outlet obstruction (Yes/No)
- ! Pseudocyst (Yes/No)
- ! Infected necrosis (Yes/No)
- ! Endoscopic drainage of pseudocyst/walled-off necrosis (Yes/No)
- ! CT-guided fine needle aspiration in case of infected pseudocyst/walled-off necrosis (Yes/No)
- ! Surgical necrosectomy (Yes-laparoscopic/Yes-open/No)
- ! Timing of surgical necrosectomy (< 2 weeks from the onset of symptoms/2-4 weeks)>4 weeks)
- ! Setting of surgical necrosectomy (Upfront/After failure of endoscopic necrosectomy/After failure of endoscopic and percutaneous necrosectomy)
- ! Cystogastrostomy (Yes-endoscopic/Yes-surgical/No)
- ! Abdominal compartment syndrome (Yes/No)
- ! Open abdomen (Yes/No)
- ! Timing of re-exploration (24-48 hours/48-72 hours/>72 hours)
- ! Bleeding (Yes/No)
- ! Bowel ischemia (Yes/No)

- ! Bowel fistula (Yes/No)
- ! Necrotizing cholecystitis (Yes/No)

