5. Risk scores	!	There are no "gold standard" prognostic score for predicting severe acute pancreatitis. Probably the bedside index of severity of acute pancreatitis (BISAP) score is one of the most accurate and applicable in everyday clinical practice because of the simplicity and the capability to predict severity, death, and organ failure as well as the APACHE-II (very complex) and other scores (1B).
6. Follow-up imaging	!	In severe acute pancreatitis (computed tomography severity index $\geq$ 3), a follow-up CECT scan is indicated 7–10 days from the initial CT scan (1C). Additional CE-CT scans are recommended only if clinical status deteriorates or fails to show continued improvement, or when invasive intervention is considered (1C).
7. Prophylactic antibiotics	!	Recent evidences have shown that prophylactic antibiotics in patients with acute pancreatitis are not associated with a significant decrease in mortality or morbidity. Thus, routine prophylactic antibiotics are no longer recommended for all patients with acute pancreatitis (1A).
8. Infected necrosis and antibiotics	! ! !	Antibiotics are always recommended to treat infected severe acute pancreatitis. However the diagnosis is challenging due to the clinical picture that cannot be distinguished from other infectious complications or from the inflammatory status caused by acute pancreatitis (2A). Serum measurements of procalcitonin (PCT) may be valuable in predicting the risk of developing infected pancreatic necrosis (1B). A CT-guided fine-needle aspiration (FNA) for Gram stain and culture can confirm an infected severe acute pancreatitis and drive antibiotic therapy but is no longer in routine use (1B).
9. Type of antibiotics	!	In patients with infected necrosis, antibiotics known to penetrate pancreatic necrosis should be used (1B). In patients with infected necrosis, the spectrum of empirical antibiotic regimen should include both aerobic and anaerobic Gram-negative and Gram-positive microorganisms. Routine prophylactic administration of antifungal is not recommended in patients with infected acute pancreatitis, although Candida spp. are common in patients with infected pancreatic necrosis and indicate patients with a higher risk of mortality (1B).

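### In severe acute pancreatitis, the CRF's first-CT classes cannot identify a scan done in the cited window of 72 to 96 hours from symptom onset, although CT timing is a compliance item

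*Combined protocol and SAP*

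**What the plan says.** The Secondary outcomes section lists the practices by which compliance will be judged. One is "Use of Ultrasound scan, CT scan, MRCP, and endoscopic Ultrasound scan (EUS) in the correct way and timing". These practices also bear on the primary objective, which is "To evaluate which items of the current AP guidelines, if disregarded, correlate with" negative outcomes. CT timing is therefore a candidate exposure as well as a descriptive item.

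The guideline text is in Table 1 (WSES 2019), item 2: "All patients with severe acute pancreatitis need to be assessed with contrast-enhanced computed tomography (CE-CT) or magnetic resonance imaging (MRI"), followed by "Optimal timing for first the CE-CT assessment is 72–96 h after onset of symptoms (1C"). This is the only window in hours for a first CT in Tables 1 to 5.

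CRF Section 7 collects "Initial diagnostic imaging (Ultrasound scan on admission/CT scan on admission/CT scan <24h/CT scan 24-48h/CT scan >48h"). Admission is named for the first two options only. The other three CT classes carry no time origin.

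Nothing else in the CRF fills the gap. Section 2 has only "Year of hospital admission for acute biliary pancreatitis (2019 Vs. 2020"). There is no admission date, symptom-onset time, onset-to-admission interval or CT date. The one field counted from onset is "Timing of surgical necrosectomy (< 2 weeks from the onset of symptoms" and later classes), in weeks and for a different procedure. The Statistical analysis section gives no rule that turns the CT classes into compliant or non-compliant.

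**The concern.** A compliance item can be scored only if the recorded classes can be mapped to the standard. Here the standard is a 24-hour window counted from symptom onset, while the record is a set of classes that ends in an open interval starting at 48 hours, from an origin that is partly unstated. If a single class holds both compliant and non-compliant scans, the compliance rate for first-CT timing in severe disease is not estimable, and any regression of outcome on that item uses a misclassified exposure.

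The missing information cannot be recovered at analysis, and a larger sample does not help. The direction of the bias cannot be assumed either: the size of the error depends on how long patients waited before admission, and that delay may itself be related to outcome.

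**Working it through.** There is no figure in the plan to reproduce. The check maps each CRF class onto the time scale of the window.

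**Inputs**
- Window: 72 to 96 h from symptom onset, severe disease (Table 1, item 2).
- Classes, in hours from their origin: on admission = 0; <24h = 0 to 24; 24-48h = 24 to 48; >48h = 48 upward (CRF Section 7).
- Delay *d* from onset to admission: not given and not collected. Assumed range 0 to 48 h, extended afterwards as a sensitivity check.

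**Formula.** A class from *a* to *b* hours after admission covers *a + d* to *b + d* hours after onset. It is early if it ends by 72 h, late if it starts at or after 96 h, in if it lies within 72 to 96 h, and mixed otherwise.

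| *d* (h) | On admission | <24h | 24-48h | >48h |
|---|---|---|---|---|
| 0 | 0: early | 0-24: early | 24-48: early | from 48: mixed (early, in, late) |
| 12 | 12: early | 12-36: early | 36-60: early | from 60: mixed (early, in, late) |
| 24 | 24: early | 24-48: early | 48-72: early | from 72: mixed (in, late) |
| 36 | 36: early | 36-60: early | 60-84: mixed (early, in) | from 84: mixed (in, late) |
| 48 | 48: early | 48-72: early | 72-96: in | from 96: late |

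**If the classes are counted from onset**, the row *d* = 0 applies to every patient. The >48h class then pools 48-72 h (early), 72-96 h (in) and over 96 h (late).

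**If they are counted from admission**, rows mix across patients. A tick in 24-48h is early at *d* = 0 to 24, mixed at 36 and in the window at 48. A tick in >48h may be early, in or late at *d* = 0, and is always late at *d* = 48. The two earliest classes stay before the window throughout.

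**Longer delay.** At *d* = 72 h, a scan on admission falls at 72 h and <24h covers 72-96 h, so both are in the window. Those classes become ambiguous only if delays beyond 48 h are allowed.

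**Would two sets of 24-hour bands suffice?** Suppose the CRF recorded onset-to-admission and admission-to-CT, each in 24 h bands. Their sum spans 24 + 24 = 48 h, wider than the 24 h window. For example, 0-24 plus 72-96 gives 72-120 h, 0-24 plus 48-72 gives 48-96 h, and 24-48 plus 24-48 gives 48-96 h. No such pair lies wholly inside 72-96 h, so the interval must be recorded directly.

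**Patients affected.** The Sample size section puts severe disease at about 20% of presentations and the minimum at 200 per year. Taking that share for the cohort, 0.20 × 200 = 40 patients per year, or 80 in both years at the minimum size.

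**The case against.** Several points on the other side stand.

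- **Only severe cases are affected.** For other patients, the tabulated first-CT advice concerns whether to scan, for example when the diagnosis is in doubt, and gives no hour window. A reader might infer that CT timing cannot be assessed in this study at all. The documents do not support that: the classes can be tabulated for everyone, and with delays up to 48 h the two earliest classes are resolved as before the window.
- **Counting from admission is an inference.** The CRF does not say it. The misfit exists under either origin, so the conclusion does not depend on the point, but the origin should be stated.
- **WSES is not named as the sole standard.** The UK table asks for CT in selected patients who deteriorate 6 to 10 days after admission, and the French audit in the Background reports CT at 48 h, so a 48 h cut has some basis. Neither rescues the item: the open class cannot isolate 6 to 10 days either, and no scoring standard is chosen.
- **Onset times in charts may be poor.** The necrosectomy field needs onset only to the week, so it does not show that hours are retrievable. This is a real cost, and an unknown category is needed.

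Three further inferences are tempting but unsupported. The rationale section names indications for CT, not timing, as a common gap. The shared ultrasound and CT field does not prove that only one may be ticked, since the CRF lists other findings that can coexist in the same format. The repeat-CT class of 7-14 days contains the cited interval ("a follow-up CECT scan is indicated 7–10 days from the initial CT scan"), so a finer split is a refinement.

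**Conclusion.** The point holds for severe acute pancreatitis and for first-CT timing. The CRF classes cannot identify a scan in the 72 to 96 hour window, whichever time origin is meant. From onset, the fault lies in >48h alone; from admission, it lies in 24-48h and >48h.

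The first result needs no assumption beyond the protocol's own text. The second assumes a delay of 0 to 48 h, which the documents neither give nor collect. The resulting error in the compliance rate or in an odds ratio cannot be quantified, because neither the delay distribution nor the distribution of scan times is available.

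The reach is limited: part of one compliance item, in roughly a fifth of patients. The definitions of 30-day mortality and morbidity, and the comparison of those outcomes between 2019 and 2020, are not touched. It merits correction because the item is listed for scoring, feeds the primary objective and is cheap to repair before data entry.

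**What to change.** Before data entry opens:

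1. Add one CRF field, the interval from symptom onset to first CT: <72 h / 72-96 h / >96 h / unknown / CT not done. A banded interval needs no calendar dates, so it fits the rule against identifiable data.
2. State the time origin of the existing <24h, 24-48h and >48h classes.
3. Record ultrasound and CT in separate fields, or state that both may be selected.
4. Write the scoring rule into the Statistical analysis section: name the guideline used as the standard, and score the 72-96 h item only in patients classed as severe in the Revised Atlanta field of CRF Section 4. Say in advance how unknown times, scans not done (Table 1 also accepts MRI) and early scans made for diagnostic doubt are handled.

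Splitting the repeat-CT class into 7-10 and 11-14 days is optional.

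If the interval cannot be collected, report CT timing by the existing classes as description and do not score it against the 72-96 h window.

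The cost is one extra field, revised response options and a short paragraph of analysis text. The main drawback is that some onset times will be unknown or imprecise; their number should be reported alongside the compliance rate.
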